5.2. LONAPEGSOMATROPIN

Lonapegsomatropin (ACP-011, TransCon hGH) is a long-acting prodrug of somatropin (hGH), designed to maintain the same mode of action and distribution as daily somatropin products, but with a once-weekly injection. Lonapegsomatropin consists of a parent drug, somatropin, that is transiently conjugated to a methoxypolyethylene glycol (mPEG) carrier (4 × 10 kDa mPEG) via a proprietary TransCon Linker (Figure 1). The carrier has a shielding effect that minimizes renal excretion and receptor-mediated clearance of lonapegsomatropin. At physiologic pH and temperature, lonapegsomatropin releases fully active, unmodified hGH via autocleavage of the TransCon Linker in a controlled manner that follows first-order kinetics.

Figure 1: Structure of Lonapegsomatropin (ACP-011)

Abbreviations: PEG10-OMe: 10 kDa methoxypolyethylene chain.

Human GH released from lonapegsomatropin has the same mode of action, volume of distribution, and cellular signaling as endogenous GH. The advantage of lonapegsomatropin in comparison to daily hGH, is the sustained exposure to hGH during the weekly dosing interval, which enhances delivery of hGH into target tissues and is important for optimal efficacy. Upon linker cleavage and release of hGH, a small molecular weight molecule,

[REDACTED] is also liberated but has shown to be rapidly cleared from systemic circulation. After release of hGH, the remainder of the linker remains covalently bound to mPEG and is cleared from the body primarily through renal clearance, as known for other high molecular weight molecules.

A predecessor molecule to lonapegsomatropin, ACP-001, contained a 4 x 20 kDa branched-chain mPEG moiety as the inactive carrier in the prodrug. Early clinical (Phase 1 and Phase 2) trials have been completed with this predecessor molecule. Subsequently, a change in the molecular weight (decrease) of the inactive branched-chain mPEG carrier molecule was introduced to generate lonapegsomatropin (ACP-011), the current version in development. This molecule contains the same hGH and TransCon Linker moieties as those incorporated into ACP-001. The only difference between the molecules is limited to the molecular weight of the inactive branched-chain mPEG carrier molecule, which is 80 kDa in ACP-001 and 40 kDa in lonapegsomatropin. The reduction in mPEG size was done to reduce the viscosity of the drug product; an extensive nonclinical and clinical program demonstrated biologic comparability of ACP-001 and lonapegsomatropin.

5.3. RELEVANT FINDINGS FROM NONCLINICAL STUDIES

Nonclinical pharmacology and toxicology studies have been conducted to support the clinical development program involving weekly subcutaneously administration of lonapegsomatropin (ACP-011) in adults with growth hormone deficiency. All pivotal nonclinical safety studies either have been or are being conducted in compliance with Good Laboratory Practices (GLP) and the program as a whole followed recommendations provided by ICH guidance and product specific guidance from health authorities. The nonclinical program has assessed both the parent prodrug and the products of autocleavage (hGH, the remainder mPEG-linker, and [REDACTED] as well as IGF-1, a biomarker for hGH.

Please refer to the current Investigator's Brochure for detailed information pertaining to the nonclinical program supporting conduct of this clinical trial.

5.4. CLINICAL EXPERIENCE

The clinical development program for lonapegsomatropin and its predecessor molecule, ACP-001, includes a total of 8 completed clinical trials: four Phase 1 trials, two Phase 2 trials, and two Phase 3 trials. The Phase 3 trials (TransCon hGH CT-301, TransCon hGH CT-301EXT, TransCon hGH CT-302) evaluated lonapegsomatropin for pediatric GHD. Please refer to the current Investigator's Brochure for detailed information pertaining to these trials.

In adults with GHD, a Phase 2, randomized, open-label, active-controlled trial of three different doses (ACP-001 0.02 mg hGH/kg, 0.04 mg hGH/kg and 0.08 mg hGH/kg) of ACP-001 administered weekly was compared to a daily hGH (Omnitrope 0.04 mg hGH/kg/week divided into 7 equal daily doses) over a period of 4 weeks. A total of 37 subjects were randomized and dosed. ACP-001 was safe and well-tolerated at all 3 doses administered during the study. There was no marked difference in the number of AEs (AEs) and injection site reactions experienced by patients treated with ACP-001 compared to those reported by the patients treated with Omnitrope, including no reported lipoatrophy or nodule formation at the injection site. Additionally, once-weekly administration of ACP-001 over a period of 4 weeks stimulated a dose-proportional response of IGF-1 at all 3 dose levels investigated in this study. Finally, treatment with ACP-001 0.04 mg hGH/kg/week, stimulated a similar IGF-1 response (AUEC) after 4 weeks of treatment to the corresponding dose of daily hGH (Omnitrope) given in this study, indicating that ACP-001 is as potent as daily hGH on corresponding weekly dose levels. Additional results for this trial may be found in the Investigator's Brochure and have been published ([Höybye 2017](#)).

In healthy adults, two Phase 1 clinical trials (ACP-011 CT-101 and TransCon hGH CT-102) have been completed with lonapegsomatropin. ACP-011 CT-101 demonstrated bioequivalence between ACP-001 and lonapegsomatropin. In TransCon hGH CT-102, lonapegsomatropin was bioequivalent in terms of hGH PK (C_{max} and AUC) and IGF-1 PD (E_{max} and AUEC) response when administered via GH Auto-Injector vs. syringe and needle.

In children with GHD, two Phase 3 clinical trials have been completed with lonapegsomatropin. The pivotal Phase 3 trial (TransCon hGH CT-301, heiGHT) in treatment-naïve prepubertal children with GHD demonstrated once-weekly lonapegsomatropin (0.24 mg hGH/kg/week) was superior to daily hGH (Genotropin 0.24 mg hGH/kg/week divided into 7 equal daily doses) for the primary endpoint of annualized height velocity (AHV) at 52 weeks.

No serious adverse event (SAEs) related to study drug were observed in either arm. No treatment-emergent adverse events (TEAEs) leading to discontinuation of study drug were observed in either arm. A low incidence of low-titer non-neutralizing antibodies was observed, comparable to that seen with daily somatropin therapies.

The single-arm Phase 3 trial (TransCon hGH CT-302, fliGHt) in predominantly treatment-experienced prepubertal children with GHD demonstrated safety and efficacy when switching from a daily hGH product to once-weekly lonapegsomatropin (0.24 mg hGH/kg/week). No drug-related discontinuations or drug-related SAEs were observed. A low incidence of low-titer non-neutralizing antibodies was observed. For both TransCon hGH CT-301 and TransCon hGH CT-302, the AE profile of lonapegsomatropin was similar to the published safety profile of daily GH therapies.

The open-label, single-arm Phase 3 extension trial (TransCon hGH CT-301EXT, enliGHten) is investigating the long-term safety and efficacy in children from the Phase 3 heiGHt and fliGHt trials receiving lonapegsomatropin. Subject retention has been high, and no safety signals have been detected to date. The study is ongoing.

Overall Clinical Summary:

Across lonapegsomatropin and ACP-001 clinical trials conducted in children and adults, there have been no AEs that led to discontinuation of the study drug, no suspected unexpected serious adverse reactions (SUSARS), and no neutralizing anti-hGH antibodies detected. The general safety and tolerability profile have been consistent with that seen with daily-administered somatropin products. Injection site reactions have generally been mild and transient and have been observed at a rate similar to that for daily somatropin. Maximum hGH serum concentrations have been comparable between equivalent weekly hGH doses of lonapegsomatropin and daily somatropin.

5.5. TRIAL RATIONALE

The primary objective of this trial is to assess the efficacy of once-weekly lonapegsomatropin compared to placebo in adults with GHD. The daily somatropin product arm is included to provide a concurrent assessment of standard of care in this patient population. GHD in adults is associated with central adiposity, diminished lean muscle mass, decreased bone mass, and reduced quality of life ([Melmed 2019](#)), and GH replacement therapy represents standard of care treatment that addresses multiple aspects of the condition ([Ho 2007](#), [Molitch 2011](#), [Japan Endocrine Society 2019](#), [Yuen 2019](#), [Kim 2020](#)). Changes in body composition are therefore an objective and sensitive endpoint that reflects biologic activity of GH and clinical efficacy. In similar placebo-controlled trials reporting trunk percent fat over a six-month period in patients with AGHD, the observed treatment effect for somatropin products has varied from -1.53% to -3.50% ([Norditropin US PI](#), [Saizen US PI](#), [Zomacton US PI](#), [Omnitrope US PI](#) and [Genotropin US PI](#)). Although there is no consensus guideline to suggest a minimally important reduction for trunk percent fat ([Hamdy 2006](#)), a change from baseline in trunk percent fat of 1.9% will be clinically meaningful as it represents a significant reduction in the key visceral adipose compartment that is metabolically important.

In addition to assessing efficacy, a treatment duration of approx. 9 months is considered adequate to assess safety and is supported by the well-characterized safety of daily somatropin products for AGHD and extensive clinical experience for lonapegsomatropin for pediatric GHD at higher doses (approximately 2-6 fold based on weight) than used in AGHD.

To assess long-term safety and efficacy, an open-label extension trial is planned. During the extension trial, all subjects will receive lonapegsomatropin.

5.6. POTENTIAL RISKS AND BENEFITS

Lonapegsomatropin is an investigational medicinal hGH prodrug product with a proposed once-weekly dosing regimen designed to overcome the inconvenience and suboptimal compliance of daily hGH injections. The safety and efficacy profile are anticipated to be comparable to currently approved daily hGH products, while maintaining exposure (C_{max} and AUC) in the optimal therapeutic range. Moreover, the exposure to hGH during the weekly dosing interval is anticipated to enhance delivery of hGH into target tissues and optimize efficacy. Obviating the need for daily injections should increase compliance and therefore long-term efficacy, which would be of great benefit to adult patients with GHD.

The safety of the subjects will be monitored by the investigators as well as the medical monitors. Stop rules have been defined in the protocol. There are no high risk procedures required and the measurement of the endpoint by dual-x-ray-absorptiometry (DXA) can be considered standard of care and is only associated with very low x-ray exposure.

In conclusion, the risk-benefit assessment for this trial is considered to be acceptable based on nonclinical, already gained clinical experience and safety data in the pediatric populations, the fact that no harming study procedures are implemented, and the fact that somatropin has been approved and used for over 30 years.

5.6.1. Risks Associated with Placebo

The objective of the study is to evaluate the efficacy of lonapegsomatropin versus placebo regarding percent change trunk fat. This placebo comparison is needed to demonstrate superiority versus no treatment, the shortest timeframe for this being 6 months maintenance (final stable dose) treatment which is commonly considered acceptable and follows similar recent clinical development programs. In addition, a double-blinded study can only be conducted using weekly administered placebo/comparator as lonapegsomatropin is administered weekly.

AGHD is caused by insufficient production of endogenous GH. The reasons for this insufficient production of GH include and are not limited to structural, infiltrative or degenerative disease in the hypothalamus / pituitary gland, hypothalamic-pituitary surgery, radiation after brain tumor, genetic disorder or traumatic brain injury (TBI). AGHD is not an acute condition, and in contrast to cortisol and thyroid hormone deficiencies not life threatening. Symptoms of AGHD are nonspecific (e.g. decrease in lean body mass and bone mineral density), metabolism and quality of life are negatively affected and establishing the diagnosis is challenging and complex.

Standard treatment of AGHD is replacement therapy (substitution) with GH, injected on a daily basis. Depending on the underlying cause, treatment mostly starts with quite some distance from the “event” (e.g. TBI, surgery, or radiation) and diagnosis to ensure stable replacement of other pituitary hormones and sufficient monitoring for tumor regrowth or tumor residual.

Based on the above, treatment initiation can take months to years. Since patients for this study must have received no GH treatment for at least 12 months prior to screening, the trial period will be a continuum of the treatment-free time for patients randomized into the placebo arm. It is to be noted that patients currently treated with GH are not eligible and no patient is asked to discontinue their GH treatment to participate in this study, only GH treatment-naïve patients or patients who have discontinued GH treatment for reasons unrelated to the study can be enrolled.

The up to 48-week treatment-free period (up to 6 weeks screening, 38 weeks treatment on placebo, and 4 weeks follow-up) is not considered to be harmful for the patients or causing significant deterioration of the condition or affecting effects of future GH treatment. The clinical manifestations of GHD are mainly of a metabolic nature: increased fat mass, decrease in muscle mass and bone mineral density, decrease in muscle strength, hypercholesterolemia, decrease in basal metabolic rate, sleep disturbances, and psychological disturbances. These clinical manifestations do not affect patient safety and are reversible under GH treatment, hence not considered causing any longer-term harm for patients. This was also concluded in a recently published study by Swedish and Dutch authors ([Postma 2020](#)).

Furthermore, during the study, the patients will be closely monitored by the investigator and the sponsors medical monitors for any signs of safety risk.

All patients completing this study will be offered to participate in an open-label extension study on once-weekly lonapegsomatropin treatment.

In conclusion, the placebo arm is needed and justified to conduct a double-blinded study and to demonstrate a robust treatment effect for lonapegsomatropin. The placebo arm is considered standard in AGHD studies without causing long-term harm to patients, diminishing future GH treatment effects, or posing a safety risk. None of the subjects are supposed to discontinue GH treatment as the study only includes subjects not treated with GH for the last 12 months or newly diagnosed with AGHD.

5.6.2. Risks Associated with the COVID-19 Pandemic

Lonapegsomatropin is a long-acting prodrug that liberates somatropin and is believed not to cause immunosuppression. Therefore, the risk of subjects being exposed to SARS-CoV-2 or suffering from COVID-19 due to treatment with lonapegsomatropin, placebo or the daily somatropin product will be similar to that of the general population. Subjects and site staff involved in this trial are expected to act according to local guidelines, recommendations, national laws, local restrictions, and hospital procedures related to COVID-19, and hereby ensure keeping the risk of viral infection low. Decisions to adjust the trial conduct will be based on the risk assessment performed by the Sponsor. The risk assessment will, as applicable, include a risk assessment of each individual trial participant. In case of local COVID-19 outbreaks several mitigating actions can be applied to ensure patient safety and data integrity: Recruitment and randomization can be postponed. For subjects already included in the study, site visits can be replaced by remote contacts as phone calls or virtual meetings, safety lab and assessments can be done locally, and study medication can be sent directly to the home of the subjects.

6. OBJECTIVES

6.1. PRIMARY OBJECTIVE

To evaluate the efficacy of once-weekly lonapegsomatropin compared to placebo at 38 weeks in adults with GHD.

6.2. SECONDARY OBJECTIVES

1. To evaluate the safety and tolerability of once-weekly lonapegsomatropin in adults with GHD.
2. To evaluate the PK of once-weekly lonapegsomatropin in adults with GHD.
3. To evaluate the PD of once-weekly lonapegsomatropin in adults with GHD.

6.3. TERTIARY OBJECTIVE

7. TRIAL DESIGN

7.1. OVERALL TRIAL DESIGN AND PLAN

7.1.1. Trial Design

This is a randomized, parallel-arm, placebo-controlled, active-controlled trial, designed to evaluate efficacy of lonapegsomatropin versus placebo. The daily somatropin product arm is included as a calibration arm to assist clinical judgement on the trial results.

Subjects will be randomized to 1 of 3 treatment arms in a 1:1:1 ratio:

- Approximately 80 subjects will be randomized to once-weekly lonapegsomatropin
- Approximately 80 subjects will be randomized to once-weekly placebo
- Approximately 80 subjects will be randomized to daily somatropin product

[figure not shown]
The trial will consist of:

- Screening Period – up to approx. 6 weeks to establish eligibility (including up to one week between randomization and the first dose to allow for logistics and shipment as needed)
- Treatment Period – (38 weeks in total), consisting of:
 - Dose Titration Period – 12 weeks of dose titration, scheduled dose titration visits will occur at Week 4, Week 8, and Week 12
 - Dose Maintenance Period – 26 weeks of maintenance treatment, trial visits will occur at Week 17, Week 28, and Week 38
 - All patients completing the treatment period will be offered to participate in an open-label extension study on once-weekly lonapegsomatropin treatment.

- Follow-up Period – (4 weeks in total), treatment free period, AEs/SAEs will be collected via phone 2 weeks after Week 38 (Week 40), an ADA sample will be taken 4 weeks after Week 38 (Week 42) The treatment free follow-up period is not applicable for subjects participating in the extension trial.

The overall trial design is shown in [Figure 2](#), a Schedule of Events can be seen in Section [18.2](#).

Figure 2: Trial Design

W = Week; N = Number;

7.1.2. Measures Taken to Minimize Bias

Once all data and results determining the subject eligibility are available and reviewed by the Investigator and Medical Monitor, the subject will be centrally randomized to 1 of 3 treatment arms: either once-weekly lonapegsomatropin, (N = 80), once-weekly placebo (N = 80) or daily somatropin product (N = 80), in a 1:1:1 ratio. In all regions except Japan, the following stratifications will be applied:

1. Dosing group.
2. In the “ ≥ 30 to ≤ 60 years old (no oral estrogen)” dosing group, randomization will be further stratified by sex.
3. Diabetes mellitus status.

In Japan, randomization will be stratified by dosing group only.

All subjects' visits should be performed in the morning to ensure fasting status. Also, DXA assessments should be performed in a similar setting (time and hydration status) at each visit, using the same approved DXA machine throughout the trial.

Additionally, all efforts will be made to keep missing data to a minimum, including the following:

1. Investigators will be trained about the importance of subject retention.
2. Investigators will be instructed to encourage subjects to complete all trial visits, until they complete the trial.

3. Investigators will be trained to collect the reason for missing data when it does occur.
4. The Informed Consent Form (ICF) will include a statement educating subjects about the scientific importance of their data, even if they discontinue study drug.
5. Special efforts will be made to provide assistance to subjects who might discontinue due to travel or cost barriers, such as offers of transportation to the clinic.
6. Visit windows allow flexibility for clinic attendance (see Section [10.2.2.1](#) and Section [10.2.2.2](#)).
7. Every effort will be made to contact subjects/caregivers or other family members to maintain contact with the clinic.

Subjects will be identified by a Subject Number (allocated at screening) consisting of 5 digits to indicate the site and 3 digits specific for the subject.

For more details on risk-based monitoring, please refer to Section [15.5.1](#).

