7.2. TRIAL SITES

The trial will be conducted at approximately 120 sites in North America, Europe, Asia, including Japan, and Oceania. All centers will be experienced endocrinology centers.

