11.2.5. Missing Causal Relationship to the Trial Drug for Adverse Events

If the causal relationship to the trial drug is missing for an AE that started on or after the date of the trial drug administration, a causality of “related” will be assigned. The imputed values for causal relationship to trial drug will be used for the incidence summary; the values will be shown as missing in the data listings.

11.2.6. Missing Data for Trunk Percent Fat at Week 38

If there are sufficient number ($n \geq 5$) retrieved dropouts in the lonapegsomatropin group, where retrieved dropouts are subjects who discontinued treatment prior to Week 38 but still have their measurements at Week 38, a retrieved dropout imputation method will be used to impute the missing measurement of non-retrieved dropouts based on known measurements from retrieved dropouts in the lonapegsomatropin group.

In the case where there are not sufficient numbers ($n < 5$) of retrieved dropouts, missing data in the lonapegsomatropin group will be imputed by copy reference imputation method for the subjects without final assessment at the Week 38 window (See [Table 2](#)) for the primary endpoint analysis ([Ayele 2014](#)).

Subjects with missing primary endpoint will have trunk percent fat value imputed using a multiple imputation model stratified by the treatment [[Schafer JL 1997](#), [Schafer JL 1999](#)]. Imputation of missing data will be conducted under assumption of missing not at random (MNAR). Missing not at random means that the data are missing is systematically related to the unobserved data, that is, the missingness is related to events or factors which are not measured.

In this analysis, intermittent missing values will be imputed to monotone missing pattern using the Markov Chain Monte Carlo (MCMC) methodology which assume that the joint distribution of the missing data and the model parameters are distributed multivariate normal. The variable list for imputations will include region (North America, Europe, Asia), dosing group and AGHD onset (adult vs. childhood), results from baseline and post baseline values for trunk percent fat.

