Then all the monotone missing values will be multiply-imputed using the imputation model built from the placebo group, i.e., assuming the missing data in the treatment group will have a profile that equals the profile of the placebo group for all time points (i.e., a copy-reference imputation). The missing data imputation will be implemented using PROC MI in SAS 9.4 with the MNAR statement. Missing data in the daily somatropin group will be imputed following the same method as the lonapegsomatropin group. Missing data in the placebo group will be imputed using the imputation model built from the placebo group.

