12.10.1. Analysis of Primary Efficacy Endpoint

Population: The target trial population comprises adult subjects with GHD and who meet the inclusion and exclusion criteria as specified in the Protocol. The analysis population is the Intent-To-Treat population as defined in Section 10.3 who have baseline trunk percent fat assessed by DXA.

Variable: The variable is the primary efficacy endpoint, change from baseline in trunk percent fat as assessed by DXA at Week 38 (Study day 240 to 295).

Handling of intercurrent events (ICEs) and missing data: Treatment policy will be used to handle ICEs where all subjects should be followed to collect the efficacy outcome regardless of intercurrent events, including treatment discontinuation or taking rescue or prohibited medications. Multiple imputation method will be used to impute the missing data if a subject is missing primary efficacy endpoint of change from baseline in trunk percent fat. See details in Section 11.2.6.

Population level summary: Treatment difference between lonapegsomatropin vs. Placebo in the change from baseline to Week 12 or Week 38.

Estimator: The difference in change from baseline at Week 38 in trunk percent fat will be estimated by the primary analysis of ANCOVA model adjusted for unequal variance, with multiple imputation for missing data as described in Section 11.2.6. The ANCOVA model will include treatment arm, region (North America, Europe, Asia-Pacific), baseline age group, gender, concomitant oral estrogen at screening in female subjects (yes vs. no), and AGHD onset (adult vs. childhood) and baseline trunk percent fat as a covariate.

For the primary efficacy analysis, a 2-sided 95% confidence interval will be calculated for the difference in least square means between the 2 treatment groups [lonapegsomatropin treatment minus placebo] at Week 38.

The absolute values and mean change from baseline of the primary endpoint variable by visit will be presented by treatment group with descriptive statistics.

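### Sex is a factor in the primary ANCOVA but is missing from both SAP imputation lists, which also label region differently: a low-severity gap that costs almost nothing to close

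*Protocol*

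**What the plan says.** **Analysis model.** SAP 12.10.1 gives the primary ANCOVA as "treatment arm, region (North America, Europe, Asia-Pacific), baseline age group, gender", followed by oral estrogen in women, AGHD onset and baseline trunk percent fat. SAP Table 3 plans separate estimates for men and women.

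**Imputation model.** SAP 11.2.6 states: "The variable list for imputations will include region (North America, Europe, Asia), dosing group and AGHD onset (adult vs. childhood"), together with "results from baseline and post baseline values for trunk percent fat". Step 2 of the tipping-point analysis in SAP 12.10.4 repeats the list. Sex is in neither.

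**How the list is used.** In the copy-reference branch of SAP 11.2.6, "Then all the monotone missing values will be multiply-imputed using the imputation model built from the placebo group". That one model fills missing values in all three arms. A different branch, based on retrieved dropouts, applies if the lonapegsomatropin arm has at least 5 of them.

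**Stratification.** Protocol 7.1.2 stratifies by sex only inside one group: in the 30-to-60-year, no-oral-estrogen "dosing group, randomization will be further stratified by sex". It adds: "In Japan, randomization will be stratified by dosing group only".

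**Regions.** Protocol 7.2 plans "approximately 120 sites in North America, Europe, Asia, including Japan, and Oceania".

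Under Protocol section 14 the SAP prevails. In any case Protocol 14.4.1 names only treatment arm and dose group for the imputation, so it does not supply sex.

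**The concern.** An imputation model should normally contain every variable that the analysis model adjusts for, or a good substitute. Otherwise the imputed values carry a weaker relation to the omitted variable than the observed values do, and the analysis then adjusts for that variable as if the relation were intact.

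Dosing group is not a good substitute for sex. Groups 2 and 3 contain both men and women, and group 1 combines oral-estrogen users of any age with everyone under 30. If men and women differ in Week 38 change after allowing for baseline and Week 12 fat, that difference is lost for exactly the subjects whose values are drawn. At stake are the primary contrast and, more directly, the male and female estimates in the forest plot.

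The region labels raise a smaller, separate question. Read literally, the imputation lists give an Oceania subject no level, so the programmer would have to choose one.

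**Working it through.** **1. The plan's own figure.** Inputs from SAP section 5: 80 per arm, difference 1.9, SD 3.7, two-sided 5%.

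- SE = 3.7 × √(2/80) = 0.585
- 1.9/0.585 = 3.248, and 3.248 − 1.960 = 1.288, which gives power 0.901 (0.898 with the noncentral t)

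The stated 90% reproduces. It is a complete-data calculation, so the choice of imputation variables does not alter it.

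**2. What omitting sex does under copy reference.** Let g be the residual sex effect (women minus men) on Week 38 change, after baseline and Week 12 fat. Let p be the share of women, and m the fraction missing by arm (L lonapegsomatropin, P placebo) and sex (F, M). Without sex in the placebo-built model, imputed values are off by about −(1−p)g for women and +pg for men. Summing over cells and subtracting arms gives:

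- primary shift ≈ −g·p(1−p)·[(mLF − mLM) − (mPF − mPM)]
- shift in women ≈ −g(1−p)·(mLF − mPF)

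If both arms have the same missingness within each sex, the two shifts are zero.

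**3. Numbers.** The documents give no dropout rate, sex mix or residual sex effect, so these are assumed: p = 0.5 and g = 1 or 2 points. Worked example, third row below, g = 1: −1 × 0.25 × [(0.25 − 0.10) − (0.10 − 0.10)] = −0.038.

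The simulation used 80 per arm, 600 trials per scenario and 10 imputations. The placebo-built imputation model had baseline and Week 12 fat, with or without sex. The ANCOVA had arm, baseline and sex, with Rubin's rules. Entries are the estimate without sex minus the estimate with sex, in percentage points, for g = 1 / g = 2.

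| Missing Week 38 scans | Primary, formula | Primary, simulated | Women, simulated | Men, simulated |
|---|---|---|---|---|
| 15% in every cell | 0 / 0 | −0.001 / +0.003 | +0.002 / +0.004 | −0.006 / +0.003 |
| Women 20%, men 10%, both arms | 0 / 0 | −0.005 / +0.002 | −0.005 / −0.004 | −0.004 / +0.007 |
| Lonapegsomatropin women 25%, all others 10% | −0.038 / −0.075 | −0.034 / −0.055 | −0.052 / −0.108 | −0.014 / −0.003 |
| Lonapegsomatropin women 30%, men 5%; placebo women 5%, men 30% | −0.125 / −0.250 | −0.103 / −0.214 | −0.087 / −0.179 | −0.118 / −0.252 |

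The simulated primary shifts are somewhat smaller than the formula because baseline fat recovers part of the sex effect. Against the SE of 0.585, the third row is 0.06 to 0.09 SE (0.034/0.585 and 0.055/0.585). The fourth is 0.18 to 0.37 SE (0.103/0.585 and 0.214/0.585). The negative sign reflects the chosen pattern, in which women lose less fat and are missing more often on lonapegsomatropin. Reversing either one reverses the sign.

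**4. Which variables can be added.** Dosing group is a function of age group and oral estrogen. Three age groups by two estrogen levels make six cells. Intercept (1) + age (2) + estrogen (1) + dosing group (2) = 6 parameters, so one empty cell makes the model singular. Sex adds one coefficient and is not determined by dosing group.

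**5. Retrieved-dropout branch.** The SAP does not say whether it uses the same list. If it does, the list already needs intercept 1 + region 2 + dosing group 2 + onset 1 + baseline 1 + Week 12 1 = 8 coefficients, from as few as 5 subjects.

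**The case against.** The strongest reply is that the omission matters little, and most of that reply stands.

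- **Imputed values do not ignore sex.** A reader might infer that they do. The lists contain each subject's own baseline and post-baseline trunk fat, which carry sex-related information. Only a residual effect is lost, and the documents give no evidence of its size.
- **Sex is not a general stratifier.** It applies in one dosing group and not in Japan, so the omission does not undo the randomization scheme.
- **A shift needs a particular pattern.** Missingness must differ by sex and by arm, and two of the three arms are double-blind. Women dropping out twice as often as men in both arms leaves the primary estimate within 0.01.
- **Other analyses limit the harm.** Sensitivity Analyses 1 and 2 require a Week 38 scan and so do not rest on imputed Week 38 values. The tipping-point analysis uses the same short list, but it shifts imputed values by up to 10 points per arm (extendable to 20), well beyond a 1 to 2 point sex effect. Sex subgroups are outside the fixed testing sequence.
- **The list may not be exhaustive.** The SAP says only what it will include. That is possible, but it is a reason to state the full list.
- **Asia is probably a label slip.** SAP 12.6, 12.10.1 and Table 3 all use Asia-Pacific. The documents do not support inferring that Oceania subjects would be dropped. The label still appears twice and should be aligned.

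What remains is that a factor of the analysis model is absent from both stated lists, and adding it is easy.

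**Conclusion.** The gap is real and of low severity. The imputation model as listed is narrower than the primary ANCOVA because it lacks sex, and its region labels do not match.

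Under copy-reference imputation, with an assumed residual sex effect of 1 to 2 points and 50% women, the primary estimate moves by about 0 if missingness is balanced between arms within each sex. It moves by 0.03 to 0.06 points under moderate imbalance and by up to about 0.2 under an extreme one. Sex-subgroup estimates move by up to about 0.11 and 0.25 in the last two cases. The stated power is unaffected.

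A reader might infer a bias in favour of lonapegsomatropin. The documents do not support that: the direction depends on which sex is missing in which arm, and no dropout pattern is given.

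The figures cover the copy-reference branch only. The simulated model left out region, dosing group and AGHD onset.

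**What to change.** In SAP 11.2.6 (copy-reference model) and 12.10.4 Step 2 (tipping point):

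1. Add sex to the imputation variables and state that the list is complete.
2. Code region as North America, Europe and Asia-Pacific, as in 12.10.1, so that Oceania subjects have a level.

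Do not add age group and oral estrogen on top of dosing group, for the reason in step 4 of the working. Do not carry the longer list into the retrieved-dropout branch. State a separate, reduced model there, since it may have only 5 donors.

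The cost is a wording change in two places and one extra coefficient in a model built on about 80 placebo subjects, fewer once missing scans are removed. No new data are needed. SAP section 1 requires analysis decisions before unblinding, so the change belongs before that point.
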